questions) is reasonable within the context of important educational and personal health information gained by the participant. The knowledge gained by this research will benefit science by determining the utility of a 3 cm or 5 cm swab for use in the parent SOLO study. If SOLO finds that self-sampling supports clinic attendance, that will benefit the performance of anal cancer screening procedures in society. For these reasons, the potential benefits of the pilot study are reasonable in relation to the anticipated benefits to the pilot study participants.

K.6 Protection of Human Subjects

K.6.1 Protection from Unnecessary Harm

MCW is responsible for protecting all individuals involved in human experimentation. This is accomplished through the IRB mechanism and the informed consent process. The IRB reviews all proposed studies involving human experimentation and ensures that the subject's rights and welfare are protected and that the potential benefits and/or the importance of the knowledge to be gained outweigh the risks to the individual. The IRB also reviews the informed consent document associated with each study to ensure that the consent document accurately and clearly communicates the nature of the research to be done and its associated risks and benefits.

K.6.2 Protection of Privacy

To ensure confidentiality, each participant is assigned an anonymous study ID, which is then used on all pilot study forms that collect participant data. Study IDs are linked to participant names and other private identifiable information in only one location, on an encrypted, firewall-protected, electronic document housed on MCW's server. All study forms are kept on the MCW server or HIPAA-compliant MCW data-sharing platform and access is restricted to authorized study personnel.

K.6.3 Protection Against Additional Risks

All procedures in the proposed pilot study involve minimal risk. The SOLO pilot uses very similar procedures as did our prior Prevent Anal Cancer Self-Swab Study. When a participant provides consent, they will be thoroughly informed of all pilot study procedures, potential risks, and benefits, and that they can discontinue participation in the study at any time without risk to subsequent care at the place(s) they receive health care. The participant, in a confidential space, will complete the consent in-person. The PI will do the initial consents while being observed by the study coordinator and other study staff; thereafter, the study coordinator and other trained study staff will perform the consents. Before signing, we will ask participants to answer three simple questions that will indicate the participant has understood the consent.

ICFs will be documented in hard copy with participant signatures kept on file in a locked cabinet at the Medical College of Wisconsin.

1. Self-swabbing. When the participant performs a self-swabbing, they will be provided instructions written at a 6th grade reading level, modeled after already-tested self-sampling instructions in the Prevent Anal Cancer Self-Swab Study.¹⁷
2. Sensitive nature of questions. This pilot study will ask sensitive questions about, sexual behavior and disease status during the computer-assisted self-interviews. Thus, names will be kept separate from coded identifiers. All computers will require a password to access files. Computer-assisted self-interviewing will be used so participants can confidentially report sensitive behaviors while minimizing feelings of shame or embarrassment discussing sexual histories. The survey items will mainly come from the

PAC Self-Swab Study surveys, which, in turn, were adapted from validated cervical cancer screening instruments.

3. **PHI access.** Access to all PHI-protected pilot study data will be limited to the PI, study coordinator, other trained and CITI-certified study staff, and clinicians. Data will be destroyed after the pilot study is completed according to federal regulations.

Persons with HIV may be vulnerable; thus, we will ensure that the highest ethical standards will be respected and followed so that benefits are maximized for a diverse set of persons while harms are minimized for all participants. For example, we include a very wide age range of people in enrollment, i.e., 35 years and older.

K.7 Required Education on the Protection of Human Subjects

In accordance with federal guidelines, all research personnel involved in these studies have completed and will periodically complete coursework in the Protection of Human Subjects as mandated by the Medical College of Wisconsin. These programs meet NIH requirements.

This study will be submitted for review to the Medical College of Wisconsin IRB prior to implementation. The IRB will oversee any human participants' concerns during the study.

K.8 Changes in the Protocol

Once the protocol has been approved by the MCW IRB, any changes to the protocol must be documented in the form of an amendment. The amendment must be signed by the investigator and approved by the IRB prior to implementation.

If it becomes necessary to alter the protocol to eliminate an immediate hazard to individuals, an amendment may be implemented prior to IRB approval. In this circumstance, however, the investigator must then notify the IRB in writing within five working days after implementation.

The IRB may provide expedited review and approval/favorable opinion for minor change(s) in ongoing studies that have the approval /favorable opinion of the IRB. The investigator will submit substantial protocol modifications to the NIH in accordance with the governing regulations. Changes to the protocol may require approval from the NIH.

K.9 Investigator Compliance

The investigator will conduct the study in compliance with the protocol given approval/favorable opinion by the IRB.

Onsite Audits: Auditing is essential to ensure that research conducted at the Medical College of Wisconsin (MCW) Cancer Center is of the highest quality and meets MCW and regulatory agency standards.

Regulatory authorities, the IRB, and/or sponsor may request access to all source documents, data capture records and other study documentation for onsite audit or inspection. Direct access to these documents must be guaranteed by the investigator, who must always provide support for these activities.

The PI will follow the procedures as outlined above, which will serve as part of the quality control procedure. To ensure the validity and integrity of pilot study data, the PI will discuss data management with the research team on a regular basis.

L DATA HANDLING AND RECORD KEEPING

The study team, including the PI, study coordinator, and other study staff will have weekly meetings. At each weekly meeting after enrollment starts, the study coordinator will provide the following information: number of participants entering the pilot study and completing cytology self-sampling, the number of dropouts, and reasons for dropout. Information about any adverse events also will be presented, including potential anxiety from cytology results. These participants will be managed using standard-of-care practices. By examining this information, the team will keep abreast of critical issues regarding reconsenting and data integrity.

- *Participant Records*. The computer-assisted self-interviews themselves will be identified only by ID number and do not contain personal identification information. Information linking the participants' identity to the study data will be kept on password-protected secure servers, while signed ICFs will be archived separately at the Medical College of Wisconsin.
- *Computer records*. Passwords and dual authentication will be used to limit access to computer records and pilot study data. No information that could lead to personal identification of participants will be included in any of the reports or given to any non-authorized person.

All raw data, data figures, data interpretation, models, and conclusions drawn from this pilot study will be managed by the principal investigator. The findings from this study may be presented at relevant conferences/meetings, published in a respectable peer-reviewed journal, or used as preliminary data in a grant application to justify extramural funding.

For any manuscript that is to be published in a journal, the role of authors/contributors, the disclosure of financial/non-financial relationships and activities, and the report of perceived conflicts of interest should largely adhere to the recommended guidelines set forth by the International Committee of Medical Journal Editors (ICMJE; Defining the Role of Authors and Contributors, Disclosure of Financial and Non-Financial Relationship and Activities and Conflicts of Interest). The PI, in consultation with the study co-investigators, should determine who will be listed as first, senior, corresponding authors, and co-authors. Study team members who have made substantial and significant intellectual contributions to the study and its findings should be listed as co-authors or, in certain circumstances, acknowledged. Funding sources and any conflict of interests, perceived or actual, should be disclosed and stated within the appropriate section of the manuscript at submission.

In accordance with the MCW Human Research Protection Program and Federal regulations FDAAA 801 and 42 CFR Part 11 (per the Final Rule, effective 1/18/2017), information about and results collected from this study are registered on ClinicalTrials.gov under NCT07085845, the clinical trial registry and results data bank operated by the National Library of Medicine (NLM) of the National Institutes of Health (NIH). All informed consent documents include a specific statement relating to the posting of study information in ClinicalTrials.gov.

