5. Ability to understand a written informed consent document, and the willingness to sign it.
NOTE: this inclusion criterion is mandatory unless a waiver of the informed consent process and document is being requested.

C.2 Exclusion Criteria

A potential pilot study subject who meets any of the following exclusion criteria is ineligible to participate in the pilot study.

1. Presence of any contraindicating severe anal disease or condition, e.g., anal stenosis.

D Pilot Study Accrual Goals and Study Duration

A total of 60 SGM will be recruited from the greater Milwaukee metropolitan area. Accrual will last for approximately 2 months.

The pilot study will reach pilot study completion within 4 months of the beginning of accrual.

E Subject Recruitment and Registration

E.1 Recruitment

Potential SGM participants will be recruited first from the group of individuals who consented into the PAC Self-Swab Study (PRO00032999) and then indicated an interest in a follow-up study (n=126). We will enroll those aged \geq 35 years. Persons reporting no sex with men during the last five years will be included if they identify as an SGM individual.

If the initial recruitment results in fewer than 60 people, we will recruit by other means:

1. Advertising on geo-located social/dating apps commonly used by older SGM, e.g., Scruff, Growlr, and Jack'd. We will run advertisements on the apps using a 25-mile radius from the city center in Milwaukee to reach people throughout the city's metro area.
2. The use of print materials in gay-friendly business and a website (mindyourbehind.org) used in the PAC Self-Swab Study. The material will mention the study is recruiting for an anal cancer screening study.

Recruitment material will be approved by an MCW Institutional Review Board (IRB). The SOLO Study Coordinator in Milwaukee will oversee recruitment activity. We will record recruitment activities.

E.2 Consenting

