Potential participants will be screened using an online computer-assisted self-interview (CASI). Those who are eligible will be asked to leave contact information. Study staff will contact eligible individuals, provide an overview of the pilot study, and invite the individual to a schedule a consenting session which will be followed by the cytology screening at the Curative Building on the MCW campus. Those who are not eligible will be thanked for their interest and provided links to vetted anal cancer education websites. Minimal Protected Health Information (PHI) will be collected in the eligibility survey.

At the consenting session staff will first ask the eligible individual to confirm their email address, name, and birthdate. The session will occur in a closed office and include information about 1) high rates of anal cancer in SGM, 2) anal cancer screening and the role of swabbing, 3) pilot study activities, and 4) the potential harms and benefits of participation. The staff member obtaining consent will emphasize that participation is voluntary and that participants can choose to join and,

if desired, leave the pilot study at any point without any repercussions. The ICF will also notify individuals that we will collect their street address to support payment using the MCW visa card.

Prior to obtaining their signature, the staff member will ask the individual if they have any questions and, if not, to briefly review their understanding of their participation by asking simple questions about the pilot study to be sure the information was clearly understood.

Individuals agreeing to provide consent will sign an ICF hard copy. It will be photocopied with the copy given to the participant.

F Pilot Study Design and Intervention

F.1 Study Design

This pilot feasibility study will use a randomized controlled trial design.

Figure 1 illustrates the pilot study design.

F.2 Randomization

Consented individuals will be randomized to either the intervention (5 cm insertion depth) or the control (3 cm insertion depth) arm using a number generator in REDCap. If the number is .0000 to .4999, the individual will be assigned to the intervention condition. If the number is .5000 to .9999, the individual will be assigned to the control condition.

The participant is considered enrolled in the pilot study when they sign a consent form and are randomized to either the intervention or control arm.

F.3 Cytology Sampling

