The investigator may withdraw a participant whenever continued participation is no longer in their best interests. Reasons for withdrawing a participant include, but are not limited to, a participant's noncompliance, or simply significant uncertainty on the part of the investigator that continued participation is prudent.

F.5.3 Replacement Policy and Data Usage

[figure not shown]
Individuals who sign the informed consent form and are randomized, but subsequently withdraw, will be replaced. Data collected from individuals that withdraw or discontinue from the study will be used.

F.6 End of Pilot Study Definition

An individual is considered to have completed the study if they have completed the post-cytology survey. Those who participated in the pilot study will not be eligible or involved in the parent SOLO study.

G Pilot Study Team, Assessments, and Procedures

G.1 Pilot Study Team Structure

G.2 Pilot Study Schedule of Events

Procedures and Events	Recruitment	Consent & Cytology Appointment	End of Pilot Study
Eligibility Screening	X		
Informed Consent		X	
Randomization and Enrollment ¹		X	
INTERVENTION			
Self-sampling with a 5 cm nylon-flocked swab		X	
CONTROL			
Self-sampling with a 3 cm nylon-flocked swab		X	
RESEARCH PROCEDURES			
Adverse Events Collection ²	(SAEs only)	AEs collected from the start of the intervention to 30 days after the end of the intervention	
Cytology Appointment Computer-Assisted Self-Interview (CASI) ³			X

¹ After an individual has signed the informed consent form and been randomized to one of the study arms, they are considered enrolled in the study.

² Refer to Section 7.2 for adverse event (AE) collection and reporting requirements.

³ The cytology CASI will be given to participants immediately after they complete cytology collection.

G.3 Pilot Study Procedures to be Conducted by Site

Activity	Milwaukee		Tampa
	Medical College of Wisconsin	Wisconsin Diagnostic Labs	Moffitt Cancer Center
Funding	Primary Award	Service contract	Service contract
Recruitment	X	-	-
Consenting	X	-	-
Randomization	X	-	-
Participant interaction	X	-	-
Obtaining PHI	X	-	-
Surveying	X	-	-
Access to PHI	X	X	-
Supplying cytology kits	X	-	-
Cytology reading	-	X	-
HPV genotyping	-	-	X

Activity	Milwaukee		Tampa
	Medical College of Wisconsin	Wisconsin Diagnostic Labs	Moffitt Cancer Center
Key personnel	X	-	-

H Statistical and Epidemiological Considerations

H.1 Pilot Study Primary Endpoints

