1. A comparison of the proportions of individuals who collect squamocolumnar cells when using a NF swab with a 5 cm vs. a 3 cm insertion depth.
2. A comparison of the proportions of individuals who collect cytologically adequate specimens when using a NF swab with a 5 cm vs. a 3 cm insertion depth.
3. A comparison of the proportions of individuals who collect adequate specimens for molecular genotyping when using the new NF swab vs. the original swab used in the PAC Self-Swab Study.
4. A comparison of the acceptability and pain performance of the new NF swab vs. the original swab.

H.2 Power for Endpoints

This pilot feasibility study does not have the power to make conclusive statements about the study endpoints.

H.3 Analysis Plan

H.3.1 Preliminary analyses

We will assess the success of randomization. For surveys, we will calculate item response rates for each arm of the study and for subgroups based on HIV status, race/ethnicity, and education.⁴³

After evaluating missing survey data, we will use multiple imputation⁴⁴ to maintain the maximum sample size if data are missing at random. Sensitivity analyses will compare results if data are not missing at random.⁴⁵

In each study arm, we will analyze frequencies of survey items, demographics, other domains, adverse events, and serious adverse events.

H.3.2 Primary Endpoint 1

The presence of cells from the squamocolumnar junction will be assessed in each specimen (Yes/No). Proportions of specimens with squamocolumnar cells will be compared for the 5 cm and 3 cm swabs.

H.3.3 Primary Endpoint 2

Cytologic adequacy is defined as the presence of ~2000-3000 nucleated squamous cells. Proportions of adequate specimens will be compared for the 5 cm and 3 cm swabs.

H.3.4 Primary Endpoint 3

The PAC Self-Swab Study molecular adequacy estimates, given study size, were quite precise with narrow confidence limits. The estimates derived from this pilot study will have wider confidence limits. The original and new swabs will be considered to have commensurate molecular adequacy if the exact confidence limits of the original PAC Self-Swab Study swab are covered by the exact confidence limits of the piloted swab.

H.3.5 Primary Endpoint 4

Each participant will receive a short cytology CASI immediately after the cytology screening to rate their acceptability of the cytology screening on a Likert scale and pain on a visual scale.³⁷ Proportions of individuals' ratings for adequacy and pain will be compared for

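### Minor, low-cost improvement: a concealed, varying-block 1:1 list would hold the two depth arms near 30:30, which the .5 cut-off rule in F.2 does not

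*Combined protocol and SAP*

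**What the plan says.** Section D sets the total: "A total of 60 SGM will be recruited from the greater Milwaukee metropolitan area". No per-arm target appears in the text available (Figure 1, the schema, is not shown).

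Section F.2 allocates "using a number generator in REDCap". The rule has two halves: "If the number is .0000 to .4999, the individual will be assigned to the intervention condition" and "If the number is .5000 to .9999, the individual will be assigned to the control condition". F.2 describes no blocking, stratification, minimisation or concealment of the sequence.

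Three other places bear on this:

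- **E.1** recruits first from 126 former PAC Self-Swab participants who were interested in a follow-up study. It then adds: "If the initial recruitment results in fewer than 60 people, we will recruit by other means".
- **F.5.3** on withdrawals: "Individuals who sign the informed consent form and are randomized, but subsequently withdraw, will be replaced". It gives no rule on the arm of the replacement.
- **H.3.1** plans a check on how well randomisation worked. H.3.2 to H.3.5 describe unadjusted comparisons of proportions.

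**The concern.** Each assignment is an independent coin flip, so the arm sizes follow a binomial distribution and can drift apart. Endpoints 1 and 2, and the 5 cm versus 3 cm part of endpoint 4, each compare two groups of about 30. The pilot's purpose includes informing the choice of insertion depth for the parent study (K.5.2), so those raw differences will be read for a decision.

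Two things could suffer. One is precision, if the split is poor. The other is comparability, if recruitment mixes former PAC participants with newcomers and the mix differs between arms by chance. Both can be addressed only before enrolment, since an assignment cannot be undone later.

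**Working it through.** The plan states no power, effect size or significance level, so there is no figure of its own to reproduce.

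**Inputs.** N = 60 (section D). The cut-offs in F.2 give 5,000 of 10,000 values to each arm, so p = 0.5.

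**Step 1: arm sizes.** Let X be the number in the 5 cm arm, X ~ Binomial(60, 0.5).

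- P(X = 30) = 10.3%
- 35:25 or worse: 2 × P(X ≤ 25) = 24.5%
- 36:24 or worse: 2 × P(X ≤ 24) = 15.5%
- 40:20 or worse: 2 × P(X ≤ 20) = 1.35%
- Mean absolute difference in arm size: 6.2 people

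**Step 2: precision.** The variance of a difference, relative to 30:30, is (1/n1 + 1/n2) / (1/30 + 1/30).

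- 36:24: (0.02778 + 0.04167) / 0.06667 = 1.042. The standard error rises by 2.1%.
- 40:20: (0.02500 + 0.05000) / 0.06667 = 1.125. The standard error rises by 6.1%.
- Averaged over the binomial: 1.018.

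For scale, assume a 50% rate in one arm, two-sided alpha 0.05 and 80% power (none of these is in the documents). The detectable difference is 33.4 points at 30:30, 33.7 at 24:36 and 34.4 at 20:40.

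**Step 3: do blocks help covariate balance?** Take a binary baseline factor. Its prevalence is an assumption. The chance that the arms differ by 20 points or more is:

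| Prevalence | Simple randomisation | Fixed 30:30, unstratified |
|---|---|---|
| 25% | 8.7% | 7.2% |
| 30% | 10.0% | 15.8% |
| 50% | 15.5% | 19.6% |

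There is no consistent gain. The differences mainly reflect discreteness: at 30:30 the gap can change only in steps of 2/30 = 6.7 points. At a 15-point threshold the order reverses for 30% prevalence (21.6% against 15.8%).

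**Step 4: do stratified blocks help?** With blocks of 4 and 6, the arms can differ by at most 3 people within a stratum at any time. With two strata and 60 people, the worst arm split is 33:27 (a difference of 3 + 3 = 6). The largest gap in the stratifying factor arises when the strata err in opposite directions, which gives 3/30 = 10 points. A simulation agrees: no gap of 15 points or more in 8,000 runs at each of 25%, 33% and 50% prevalence, against 21% to 25% under simple randomisation.

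**Step 5: the price.** In a known fixed block of 4 there are 6 orderings. Two of them (AABB, BBAA) have two forced assignments and four have one, so the predictable share is (2×2 + 4×1) / (6×4) = 1/3. For a known fixed block of 6 it is 1/4. Under F.2 as written it is 0. This matters because F.3 has staff prepare kits with different labels and visibly different swab marks.

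**The case against.** The strongest reply is that nothing here is wrong. Simple randomisation is valid and unbiased, the text promises no 30:30 split, and H.2 already concedes: "This pilot feasibility study does not have the power to make conclusive statements about the study endpoints". A 2% rise in standard error at 36:24 changes no conclusion in such a study. Endpoint 3 and the new-versus-original part of endpoint 4 compare with the earlier study, so balance between the depth arms matters little there. All of this stands, and it is why the point is minor.

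The stratifier may also be empty. Section A plans to test the swab in 60 former PAC participants, and E.1 looks elsewhere only if they fall short. The documents say these people consented to the earlier study. They do not show that prior participation, or HIV status, affects specimen quality or acceptability. This stands too, so stratification is conditional.

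A reader might infer three stronger things:

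- **That permuted blocks alone would remove prognostic imbalance.** Step 3 shows they would not.
- **That blocks would return a replacement to the arm that lost someone.** They would not, because the replacement takes the next slot on the list. Exposure is probably small anyway, since sampling follows directly on randomisation (F.3).
- **That the change is free.** Step 5 shows a cost in predictability.

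What the reply does not answer is that near-equal arms are easy to secure before enrolment and that F.2 does nothing to secure them.

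**Conclusion.** The point holds as a cheap, minor improvement, not as an error. Under F.2 the depth arms will be 36:24 or worse 15.5% of the time and 40:20 or worse 1.35% of the time. The cost in variance is 1.8% on average, 4.2% at 36:24 and 12.5% at 40:20. It falls only on endpoints 1 and 2 and the 5 cm versus 3 cm part of endpoint 4.

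The arm-size figures rest only on N = 60 and p = 0.5, both from the protocol. Replacements would take the number randomised slightly above 60 without changing the picture. The covariate figures rest on assumed prevalences. The benefit of stratifying rests on two further assumptions: that people from outside PAC are enrolled, and that prior participation is prognostic. A reader should not conclude that the planned comparisons are biased or that the pilot fails its purpose. The documents support neither.

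**What to change.** Replace the cut-off rule in F.2 with a pre-loaded 1:1 permuted-block list in REDCap. Use randomly varied block sizes (for example 4 and 6), and conceal the list and the block sizes from the staff who consent participants and hand out kits. Add that, if recruitment moves to the other means in E.1, the list is stratified by prior PAC Self-Swab participation (yes/no). Because strata must be in place before the first assignment, load both stratum lists at the start. If every participant comes from PAC, the second list is simply unused.

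The cost is one paragraph in F.2 and one list upload before enrolment. The downside is that some assignments near block ends become predictable to staff who can see which kits have been used. Varied sizes and concealment reduce this but do not bring it to zero.

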The cytology sampling will occur immediately after randomization. In preparation, staff will have created two cytology collection kits (labeled as Kit A or Kit B) each containing swabbing instructions, a swab, ThinPrep vial, and gloves. Kit A and Kit B will have identical contents except that Kit A will have a swab with a colored mark 5 cm from the swab tip and Kit B will have a swab with a colored mark 3 cm from the swab tip.

Clinical staff will review the sampling instructions with the individual and then show them to a bathroom in Curative with a locking door where they will do the self-sampling with sampling instructions available. Individuals will be instructed to take the cap off the vial, put on gloves, remove the swab from the packaging, hold the swab at the marker on the shaft of the swab (which corresponds to either 3 cm or 5 cm), get in a comfortable position, insert the swab gently all the way to the mark, begin to twirl the swab clockwise and counterclockwise, and apply pressure to the anal canal walls, while removing the swab as they count slowly to 10.

[figure not shown]

Figure 1. Pilot study schema.

After swabbing, the participant will put the swab in 20 mL of PreservCyt® solution, agitate and twirl it in the solution for 10 seconds, and then remove the swab while pressing against the sides of the vial. The swab will be discarded, the vial cap replaced, and the vial inserted back into the Kit and returned to the staff member. Participants will be instructed to wash their hands.

Participants will complete a short CASI in the consenting office in private on their phone (or hard copy if they prefer) immediately after their self-sampling to assess the swabbing experience, including discomfort and pain, using validated questions. Clinic staff will assist individuals with technology limitations. Participants will then receive \$40.

For those who do not show up for their consenting and cytology appointment, a member of the study team will contact them twice to reschedule within 2 months of their original appointment date.

F.4 Kit Processing, Cytopathology, and Genotyping

Staff will walk the cytology kit to the MCW Tissue Bank who will process the PreservCyt liquid by removing a 0.5 mL aliquot for HPV genotyping. The remaining specimen will be kept in the original vial for cytopathology.

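### Staff review the sampling technique after randomisation, with no masking or script described, so the review could differ by arm; giving the common review before the draw is a cheap improvement

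*Combined protocol and SAP*

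**What the plan says.** Section F.2 (Randomization) assigns consented individuals by a REDCap random number: "If the number is .0000 to .4999, the individual will be assigned to the intervention condition", and otherwise to control. Section F.3 (Cytology Sampling) begins: "The cytology sampling will occur immediately after randomization". It then describes the kits: "staff will have created two cytology collection kits (labeled as Kit A or Kit B) each containing swabbing instructions", together with a swab, a vial and gloves. On how they differ it says: "Kit A and Kit B will have identical contents except that Kit A will have a swab with a colored mark 5 cm" from the tip, while Kit B's mark is at 3 cm.

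The next step is the spoken review: "Clinical staff will review the sampling instructions with the individual and then show them to a bathroom in Curative with a locking door". The participant then samples alone with the instructions to hand. Depth is conveyed by the mark: "insert the swab gently all the way to the mark". The technique also has the participant "begin to twirl the swab clockwise and counterclockwise, and apply pressure to the anal canal walls" during a slow withdrawal over a count of ten.

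Neither section describes masking of the staff who give the review, or a script for what they say. Figure 1, the study schema, is not available in the text reviewed, so the order is taken from the prose.

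**The concern.** The spoken review is a staff input that sits between allocation and outcome. Twirling, wall pressure and slow withdrawal depend on effort and plausibly affect cell yield, on which endpoints 1 (squamocolumnar cells) and 2 (cytologic adequacy) rest. How discomfort is described beforehand can shape the pain and acceptability ratings compared by depth in endpoint 4. Section A states a directional expectation that 5 cm will give the better specimen, and H1 and H2 repeat it. A reviewer aware of the arm could, without intending to, teach one arm more fully than the other.

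The analysis could not separate such a difference from an effect of depth. The result matters beyond the pilot, because section K.5.2 says the work will establish how useful a 3 cm or 5 cm swab is for the parent SOLO study. Endpoint 3 compares the new swab with the original one, not the two depths, and is not exposed in this way.

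**Working it through.** **No stated figure to reproduce.** Section H.2 gives no power, error rate or effect size, and the point concerns the order of procedures. The main check is therefore a reading of the sections side by side.

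1. *Order.* F.2 ends with allocation. F.3 opens by placing sampling straight after it and only then describes the staff review. The natural reading is consent, randomise, review, self-sample. Section A mentions written instructions after consent but does not place them before or after the draw.
2. *Is the order needed?* The kits differ only in the position of the mark, and the instruction sheet is one of the shared contents. The sheet refers to the mark, not to a length. The core of the review can be given without knowing the arm.
3. *Could the reviewer know the arm?* Staff make the kits, there are two fixed labels, and the sheet under review is packed in the kit. Section G.3 gives randomisation, participant contact and kit supply to the same institution. This makes knowledge likely, but the text does not state it.
4. *Which outcomes?* H.3.2 and H.3.3 compare proportions by depth; H.3.5 does so for ratings. All are downstream of the review.

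**Illustration of sensitivity.** The only input from the documents is the total: "A total of 60 SGM will be recruited from the greater Milwaukee metropolitan area", so about 60 / 2 = 30 per arm. The success rates and coaching shifts are assumptions.

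Let X5 ~ Binomial(30, p + b) and X3 ~ Binomial(30, p), with no true depth effect and b the advantage from fuller coaching in the 5 cm arm. The chance that the 5 cm arm looks better, with ties split, is P(X5 > X3) + ½ P(X5 = X3).

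| p | b | P(X5 > X3) | P(tie) | Looks better, ties split |
|---|---|---|---|---|
| 0.60 | 0 | 0.448 | 0.105 | 0.500 |
| 0.60 | 0.05 | 0.606 | 0.098 | 0.655 |
| 0.60 | 0.10 | 0.753 | 0.077 | 0.791 |

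For p from 0.50 to 0.80, the chance that the 5 cm arm is strictly better is 0.60 to 0.63 when b = 0.05 and 0.74 to 0.82 when b = 0.10.

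The 95% half-width of the difference is 1.96 × √(2p(1 − p)/30). At p = 0.60 this is 1.96 × √(0.48/30) = 1.96 × 0.1265 = 0.248. It is 0.253 at p = 0.50 and 0.202 at p = 0.80. A shift of 5 or 10 points lies well inside that noise, so the data could not reveal it.

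**Effect of the fix.** Moving the review leaves N, the 1:1 allocation and the single visit as they are. Power is therefore also unchanged: with two-sided 5% assumed, it is 0.39 for 60% v 80% before and after. Teaching given before the draw cannot depend on an arm not yet drawn, and simple randomisation keeps the next arm unpredictable.

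**The case against.** The strongest reply is that the reviewer's knowledge of the arm is assumed. F.3 does not say that the person giving the review made the kit, drew the allocation or holds the kit while talking. That stands: the exposure comes from the absence of described masking, not from a stated open review.

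Second, safeguards exist. The written sheet is common to both arms, pitched at a 6th grade reading level and modelled on tested instructions (K.6.3). It is available during sampling, which is done alone, and the survey is completed in private. Recruitment goes first to people from the earlier PAC Self-Swab Study, who may already know the technique (E.1). These limit how much a short talk could shift yield, but they do not standardise what is said aloud.

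Third, the expectation is not all in one direction. Section A allows that deeper insertion may affect acceptability without improving the specimen, and H4 expects similar pain and acceptability by depth. For endpoint 4 the direction of any bias is therefore unclear.

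Fourth, H.2 disclaims conclusive statements, and the assumed shifts are not evidence. Both are fair. The disclaimer does not remove the concern, though, because the observed direction may still inform the choice for SOLO.

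Fifth, participants must hold the swab at its mark, so some orientation after allocation is legitimate. This also stands and is kept in the fix.

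**Conclusion.** The point holds as an avoidable opening for performance bias. As F.2 and F.3 are written, the spoken review follows allocation, no masking or script is described, and nothing in the common instructions requires that order. The comparisons exposed are endpoints 1, 2 and the depth part of endpoint 4. The size is unknown; the probabilities above rest on assumed rates and shifts and show sensitivity only.

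Three stronger conclusions might be inferred and are not supported:

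- *That staff do coach the arms differently, knowing the kit.* The documents show neither the knowledge nor a difference.
- *That the review is the only staff contact after allocation.* Kit hand-over and help with the survey for those with technology limitations also follow it, and the second touches endpoint 4 directly.
- *That the present order will produce many withdrawals after randomisation.* The consent session (E.2, K.6.3) already covers procedures and harms and checks understanding, so there is little reason to expect people to decline only at the review.

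This is a cheap improvement to a pilot that is not powered for its endpoints, not a flaw that invalidates it.

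**What to change.** In F.2 and F.3, set the order as follows:

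1. Consent.
2. Review of the common instructions from a short script that refers to the mark and names no depth.
3. The REDCap draw.
4. Hand-over of the closed kit.

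Limit contact about technique after allocation to a scripted orientation to the mark and to answering participants' questions from the same instruction sheet.

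The cost is a loose copy of the instruction sheet for the review, a short script and small edits to the two sections. There is no change to sample size, allocation, number of visits or power. The change does not remove other staff contact after allocation, such as help with the survey, nor the participant's own view of the mark.
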